5.3.2 HANDLING OF PARTICPANT WITHDRAWALS OR TERMINATION

Approximately 30 subjects will be enrolled in the study. Subjects will be encouraged to complete the study and all assessments. However, subjects may voluntarily withdraw at any time, and the investigator may discontinue individual subjects from the study at any time. For subjects who withdraw consent from the study, no study procedures will be done thereafter. For those that withdraw from receiving the study agent, follow-up visits and the safety phone follow-up are to occur as per the protocol. Excluding cases of medical emergency, but prior to the discontinuation of a subject from the clinical study for disease worsening, the study investigator should discuss each case of discontinuation with the sponsor and/or the medial monitor.

The subject withdrawal criterion below should be used to assess worsening or disease progression. In such cases, a documented assessment by the principle investigator is required, and subjects with clinically significant disease progression should be considered for withdrawal from the study and subsequent initiation of standard of care:

- A BCVA loss of ≥ 5 letters from baseline
- New macular subretinal hemorrhage
- Investigator discretion based on acute worsening of underlying disease or substantial risk to further participation in the study

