13.2 Treatment Exposure

Extent of exposure will be calculated in days using the following:

$$\text{Extent of Exposure (days)} = [\text{Date of last dose} - \text{Date of first dose}] + 1$$

Extent of treatment exposure (days) and the total number of doses received for each subject exposed to IMP will be summarized with continuous descriptive statistics using the Safety set. A subject listing of treatment exposure will also be produced.

14. Analysis of the Primary Endpoint

The primary endpoint is the mean change from baseline (Visit 2 / Day 1) to end of treatment (Visit 8 / Day 43) in BCVA letter score of the study eye as measured by the ETDRS testing method using the Evaluable set. BCVA will be measured at the beginning of every study visit and change from baseline for each subject will be calculated as follow-up visit minus baseline visit. Quantitative summary statistics will be used to summarize the BCVA letter score and change from baseline at each visit. A two-tailed, one-sample t-test will be used to assess the mean change from baseline in BVCA letter score at each visit, in which the change from baseline BCVA letter score will be compared to a reference value of zero. The following SAS code will be used to run the one-sample t-test:

```
PROC TTEST H0=0 ALPHA=0.20 DATA=INDATA;
  VAR BCVA_CHG;
RUN;
```

where

- *INDATA* is the name of the input dataset;
- *BCVA_CHG* is the change in BCVA from baseline to the follow-up visit.

A mixed model accounting for repeated measures will also be used to analyze BCVA. This model will include the change from baseline in BCVA letter score as the response variable and baseline BCVA letter score, smoking status and visit as explanatory variables for adjustment. LS means for each visit will be calculated along with corresponding 95% CIs and p-values. SAS code to implement this repeated measures mixed model is as follows:

```
PROC MIXED DATA=INDATA;
  CLASS SUBJID SMOKE VISIT;
  MODEL CHG = BASELINE SMOKE VISIT / DDFM = KR SOLUTION;
  REPEATED VISIT / SUBJECT=SUBJID TYPE=UN;
  LSMEANS VISIT / CL;
RUN;
```

where

- *INDATA* is the name of the input dataset sorted by *SUBJID* and *VISIT*;
- *SUBJID* is the subject ID number;
- *SMOKE* is the subject's smoking history (Never smoked, Ex-smoker, Currently smokes);
- *VISIT* is the visit at which the BCVA letter score was collected;

- *CHG* is the change from baseline in the BCVA letter score;
- *BASELINE* is the baseline BCVA letter score;

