The Kenward-Roger method will be used to determine denominator degrees of freedom. An unstructured variance-covariance matrix will be used for the above repeated measures model. If the model does not converge using the unstructured matrix, the first order autoregressive structure and the compound symmetry structure will be employed, in that order.

The above analyses will be repeated on the PP set as a sensitivity analysis.

Additionally, the number of subjects with change from baseline in BCVA letter score for the following categories will be summarized with counts and percentages:

- ≥ 15 letters;
- ≥ 14 and ≥ 10 letters;
- ≥ 9 and ≥ 5 letters;
- ≥ 4 and ≥ -4 letters;
- ≥ -5 and ≥ -9 letters;
- ≥ -10 and ≥ -14 letters;
- ≤ -15 letters.

BCVA results will also be presented in a data listing. BCVA results in the fellow eye are not included in the analyses but will be included in the listings. BCVA will also be summarized by visit using box plots.

15. Analysis of the Secondary Endpoints

The analyses for secondary endpoints (incidence, seriousness and severity of AEs) will be discussed in the next section as part of the safety analyses. There is no secondary efficacy endpoint for the study.

16. Safety Analyses

Safety will be assessed for the following endpoints using the Safety set:

- Incidence, seriousness, and severity of AEs;
- Observed slit-lamp biomicroscopy values;
- Observed intraocular pressure (IOP) values;
- Changes from baseline in clinical laboratory values;
- Changes from baseline in physical examination;
- Changes from baseline in vital signs.

Adverse events will be presented using frequencies and percentages of subjects.

Other safety endpoints including slit-lamp biomicroscopy, IOP, clinical laboratory values, physical examination, and vital signs will be summarized using descriptive statistics. Changes or shifts from baseline will also be summarized where appropriate. Assessments performed by eye (study eye and fellow eye) will be summarized separately. No statistical inferential testing will be performed for safety variables.

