- Presence of Hemorrhage in the PED (including area of the hemorrhage) as measured by FP/FA
- Presence of Disciform Scar/Retinal Fibrosis as measured by FP/FA

18. Interim Analyses

Continuous data monitoring will be performed. One interim analysis will be performed when two-thirds of all entered subjects have reached Day 15 (Visit 4). The interim analysis will include only a subset of the secondary endpoint (i.e., accumulated AE information).

Recruitment into the trial will be stopped if the interim analysis shows relevant safety problems with ALK4290. No formal futility analysis will be conducted.

19. Pharmacokinetic Analysis

A separate PK plan will be created to describe details pertinent to the analysis of collected PK data.

20. Biomarker Analysis

A separate biomarker plan will be created to describe details pertinent to the exploratory analysis of collected biomarker data.

21. Changes from Protocol-Stated Analyses

Not applicable.

22. References

Not applicable.

23. Revision History

Documentation of revision to the SAP will commence after approval of the Final version 1.0.

24. Tables

Tables that will be included in the topline delivery are shown in boldface font and the tables, listings, and figures for the interim analyses are italicized.

Table Number	Title	Set
14.1.1	Subject Disposition	All Subjects
14.1.2	Demographics and Baseline Characteristics	ITT Set
14.1.3.1	Ocular Medical History	ITT Set
14.1.3.2	Non-Ocular Medical History	ITT Set
14.1.4.1	Ocular Concomitant Medications	ITT Set
14.1.4.2	Non-Ocular Concomitant Medications	ITT Set
14.1.5	Compliance with Study Drug	Safety Set
14.1.6	Exposure to Study Drug	Safety Set
Primary and Exploratory Efficacy Analyses		
14.2.1.1	Summary of Study Eye BCVA Letter Score and Change from Baseline at Scheduled Visits	Evaluable Set
14.2.1.2	Summary of Study Eye BCVA Letter Score and Change from Baseline at Scheduled Visits	PP Set
14.2.1.3	Categorical Summary of Study Eye BCVA Letter Score Change from Baseline at Scheduled Visits	Evaluable Set
14.2.2.1	Summary of Study Eye Central Subfield Thickness (μm) and Change from Baseline as Measured by SD-OCT at Scheduled Visits	Evaluable Set
14.2.2.2	Summary of Study Eye Central Subfield Thickness (μm) and Change from Baseline as Measured by SD-OCT at Scheduled Visits	PP Set

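### The five middle BCVA change categories in SAP 14 overlap as printed and leave losses of 11 to 14 letters in no row; separately, the supportive mixed model weights three smoking groups equally

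*SAP*

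**What the plan says.** **Categories.** SAP Section 14 defines change as follow-up minus baseline, so losses are negative, and asks for counts and percentages in seven categories. The top row is 15 letters or more and the bottom row is -15 or less. The printed middle rows include "≥ 14 and ≥ 10 letters", "≥ 4 and ≥ -4 letters", "≥ -5 and ≥ -9 letters" and "≥ -10 and ≥ -14 letters"; the remaining one, with bounds 9 and 5, has the same form. The rows feed Table 14.2.1.3 in SAP Section 24, "Categorical Summary of Study Eye BCVA Letter Score Change from Baseline at Scheduled Visits", on the Evaluable set. Nothing else in the SAP defines these bins.

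**Mixed model.** After the one-sample t-test against zero, SAP Section 14 adds: "A mixed model accounting for repeated measures will also be used to analyze BCVA". The model has baseline BCVA, smoking history (a CLASS variable with levels never, ex and current) and visit, without interactions. Visit means come from "LSMEANS VISIT / CL", with no weighting option. SAP Section 17.1 has the quantitative exploratory endpoints analysed in a similar manner to the primary one. SAP Section 11.1 does not list smoking status among the demographic variables.

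**The concern.** A row with two lower bounds has only one effective bound, the larger. The five middle rows therefore nest instead of dividing the scale, and a gap opens above the bottom row. Table 14.2.1.3 is the only categorical gain/loss table for the primary endpoint. Its loss rows are where a reader would look for the protocol's own worsening mark in Section 5.3.2, "A BCVA loss of ≥ 5 letters from baseline". Programmed as printed, those rows would include subjects with no loss and omit losses of 11 to 14 letters.

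The mixed-model point is of a different kind. In a two-arm trial with no treatment-by-smoking term, the smoking weights cancel from the treatment difference. Here there is one arm and the visit LS mean is itself compared with zero, so the weights enter the estimate, its interval and its p-value. The t-test beside it averages the subjects actually analysed. The two analyses can therefore target different means without the SAP saying so.

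**Working it through.** **1. The categories.** The documents give no figure to reproduce, and the check of the printed text needs no assumption about the data. The intended rows are inferred from the printed bounds.

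| Row | Printed bounds | Reduces to | Evidently intended |
|---|---|---|---|
| 1 | ≥15 | ≥15 | ≥15 |
| 2 | ≥14, ≥10 | ≥14 | 10 to 14 |
| 3 | ≥9, ≥5 | ≥9 | 5 to 9 |
| 4 | ≥4, ≥-4 | ≥4 | -4 to 4 |
| 5 | ≥-5, ≥-9 | ≥-5 | -9 to -5 |
| 6 | ≥-10, ≥-14 | ≥-10 | -14 to -10 |
| 7 | ≤-15 | ≤-15 | ≤-15 |

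Both sets of rules were applied to every integer from -100 to 100.

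- Printed rules: 0 falls in rows 5 and 6; +12 in rows 3 to 6; +20 in rows 1 to 6; -6 to -9 only in row 6, the next worse row; -11 to -14 in none.
- From -14 to +14, only 14, 9, 4, -5 and -10 reach their intended row, so 29 - 5 = 24 miss it. Only -10 and values of -15 or below are counted once and in the right row.
- Intended rules: every integer falls in exactly one row.

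To show the size in a table, assume change is normal with mean -3, 0 or 3 and SD 5, 8 or 12, rounded to whole letters. The documents give no mean or SD. Over these nine cases:

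- the printed rows sum to 174% to 287%;
- row 5 shows 58% to 96% where 6% to 29% is correct;
- 0.3% to 10% of subjects are in no row.

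**2. The LS-mean weights.** With smoking as a CLASS main effect and no weighting option, the default gives each level present equal weight, 1/3 if all three occur. About 25 evaluable subjects is from SAP Section 6. The smoking split, any smoking effect and the within-subject correlation are not in the documents and are assumed. Further assumptions are complete Visits 3 to 8, correlation ρ of 0.5, 0.7 or 0.9, and baseline left out.

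The measure is the generalised least squares variance of the Visit 8 mean with weights 1/3 each, divided by that with subject-share weights. Under compound symmetry with six visits this is 1 + f(R - 1), where R = (n/9) × Σ(1/n_k) and f = (1 + 5ρ)/6. For 12/9/4, R = (25/9)(1/12 + 1/9 + 1/4) = 1.23. At ρ = 0.5, f = 3.5/6 = 0.583, giving 1 + 0.583 × 0.235 = 1.14.

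| Split (never/ex/current) | Compound symmetry, ρ = 0.5/0.7/0.9 | AR(1), ρ = 0.5/0.7/0.9 | CI wider by |
|---|---|---|---|
| 8/8/9 | 1.00 throughout | 1.00 throughout | 0% |
| 12/9/4 | 1.14/1.18/1.22 | 1.09/1.13/1.19 | 4% to 10% |
| 14/9/2 | 1.52/1.67/1.82 | 1.34/1.48/1.71 | 16% to 35% |

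The last column is the square root of the ratio minus 1.

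The shift of the estimate is (1/3 - share of current smokers) × (difference between current smokers and the rest). For a difference of 2 to 5 letters its absolute size is:

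- 8/8/9: |1/3 - 9/25| × 2 to 5 = 0.05 to 0.13 letters;
- 12/9/4: (1/3 - 4/25) × 2 to 5 = 0.35 to 0.87 letters;
- 14/9/2: (1/3 - 2/25) × 2 to 5 = 0.51 to 1.27 letters.

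If smoking is unrelated to change, the shift is 0 at any split.

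**3. The primary test.** The t-test code uses only the numeric change. Neither the categories nor smoking enters it.

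**The case against.** On the categories, the case against is that the intent is plain, that the signs may have been altered in reading the PDF, and that sums far above 100% would be noticed before release. The table is also descriptive: SAP Section 6 says the study is not powered for efficacy differences, every BCVA score is listed (Listing 16.2.6.1), and means and box plots by visit are planned. Losses of more than 15 letters are a separate event of special interest. Because the table uses the Evaluable set, subjects who stop before three weeks are absent whatever the signs. These points limit the consequence and stand. They do not remove the defect: this list is the only definition of the table's rows. The last bullet of the same list does print a less-or-equal sign, so wholesale loss of that symbol is unlikely, though the source file should be checked. A programmer who coded the rows as an ordered cascade would avoid double counting but would still misassign changes.

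On the mixed model, equal weighting is a software default and not SAP wording, the model is additional to the t-test, and the size rests on assumed splits. With roughly balanced groups it is nil. If Visits 9 and 10 are also modelled, the AR(1) low ends fall to 1.07 (12/9/4) and 1.27 (14/9/2). The ratios use simple covariance structures, not the unstructured matrix that the SAP tries first. Carry-over to the exploratory endpoints is inferred from the word similar in SAP Section 17.1. All of this is fair, and it is why the point is offered as an improvement.

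**Conclusion.** The categories are wrong as written and should be corrected before programming. That 24 of the 29 changes between -14 and +14 miss their row, and that -11 to -14 have none, follows from the printed signs and the evident intended bins. The percentages in the working are illustrations under a normal assumption and literal programming.

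The LS-mean weighting is a legitimate but unstated choice of target, and it matters only when the smoking groups are unequal. With six visits the Visit 8 interval is 0% to 35% wider across the three assumed splits. The estimate moves by at most about 1.3 letters in the assumed range, and not at all if smoking is unrelated to change. For CST and for IRF, SRF and PED height the same weights would apply if SAP Section 17.1 is taken to include the mixed model.

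Neither point changes the primary t-test.

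**What to change.** Rewrite the seven rows as: ≥15; 10 to 14; 5 to 9; -4 to 4; -9 to -5; -14 to -10; ≤-15. Check the SAP source file for a lost sign at the same time.

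For the mixed model, keep smoking as a covariate and set its coefficients to each level's share of the analysed subjects. This can be done with an ESTIMATE statement for each visit, holding baseline at its mean, or with the OM option pointed at a data set with one row per subject at every model visit. OM should not be run on the analysis records, because subjects with missed visits would then count for less. For example, if two current smokers of 25 have 3 of 6 visits and the rest are complete, their weight is 6/(6 + 23 × 6) = 6/144 = 4.2% instead of 2/25 = 8.0%. Do the same for the Evaluable and Per Protocol sets.

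Add smoking status to the baseline table so that the split is visible.

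The cost is five signs, a few lines of code and one characteristic in the demographics table. No extra data are needed and patients are not affected.

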16.1 Adverse Events

AEs are defined as any untoward medical occurrence associated with the use of an IMP in humans, whether or not considered IMP-related. All AEs, serious and non-serious, occurring during the course of the clinical trial (i.e., from signing the informed consent through the follow-up period) will be collected, documented, and reported. All AEs that occur or worsen on or after the first use of IMP will be considered as treatment-emergent AEs (TEAE). Reported AEs that begin prior to the first dose of IMP are classified as non-TEAEs; these will only be included in subject listings and not included in summary tables.

When reporting an AE, the event description should use the best matching terminology describing the event as found in the Common Terminology Criteria for Adverse Events (CTCAE v4.03). Standardized terms from the CTCAE will be used to categorize events for reporting to regulatory authorities using the Medical Dictionary for Regulatory Activities (MedDRA, v. 21.0).

The severity of all reported AEs are graded by the investigator into one of the following five (5) CTCAE categories:

- Grade 1 (Mild)
- Grade 2 (Moderate)
- Grade 3 (Severe)
- Grade 4 (Life-Threatening)
- Grade 5 (Death)

The relatedness of IMP to AE will be classified as definite, possibly, or unrelated. Documentation of AEs will include start date, end date, seriousness, severity, relatedness, whether or not medication was required, outcome, and action taken with the study agent.

A serious adverse event (SAE) is defined for this protocol as any AE that meets one or more of the following criteria:

- A death (CTCAE Grade 5 event) occurring during the study, whether or not considered treatment-related;
- A life-threatening event (CTCAE Grade 4);

- An event requiring inpatient hospitalization or prolonged hospitalization due to the adverse event;
- An adverse event resulting in a significant, persistent, or permanent change, impairment, damage or disruption in the participant's body function or structure, physical activities or quality of life;
- An event that otherwise required a medical or surgical intervention to preclude permanent impairment or damage (excluding unrelated elective or cosmetic procedures).

An AE of special interest (AESI) is defined for this protocol as any the following outcomes:

- Hepatic injury defined by the following alterations of liver parameters:
 - For subjects with normal liver function at baseline an elevation of aspartate aminotransferase (AST) and/or alanine aminotransferase (ALT) \geq 3-fold the upper limit of normal (ULN) combined with an elevation of total bilirubin \geq 2-fold the ULN measured in the same blood draw sample;
- Abrupt decrease of BCVA ($>$ 15 letters lost from baseline);
- QTc interval prolongation ($>$ +50 ms from baseline and $>$ 450 ms).

An overall tabular summary of TEAEs will be presented that includes the number and percentage of subjects who experienced at least one TEAE. These summaries will also include breakdowns of TEAEs further categorized as ocular or non-ocular, and within these categories as drug-related TEAEs, TEAEs with CTCAE Grade 3/4/5, drug-related TEAEs with CTCAE Grade 3/4/5, TEAEs with an outcome of death, serious TEAEs, drug-related serious TEAEs, TEAEs leading to discontinuation of IMP and drug-related TEAEs leading to discontinuation of IMP.

Furthermore, the number and percentage of subjects with TEAEs by SOC and PT; by SOC, PT and maximal severity; by SOC and PT for TEAEs; by SOC and PT for SAEs; and by SOC and PT for TEAEs leading to subject withdrawal will be presented. Separate summaries will be provided for ocular and non-ocular TEAEs (including systemic). Adverse events of special interest will also be summarized by SOC and PT. These summaries by SOC and PT will be at the subject level. If a subject reports the same PT multiple times within the same SOC, that PT will only be counted once within that SOC. As with the PT, if a subject reports multiple conditions within the same SOC, that SOC will only be counted once.

All AEs (including non-TEAEs) will also be presented in subject listings.

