7.2.1.2.3 Grading Severity of Adverse Events

The investigator must grade the severity of all reported adverse events into one of the following five (5) categories:

- Grade 1 (Mild)
- Grade 2 (Moderate)
- Grade 3 (Severe)
- Grade 4 (Life-Threatening)
- Grade 5 (Death)

The standardized CTCAE severity grading scales for the specific type of adverse event reported must be used when a matching CTCAE term is available. The highest severity grade experienced for the event should be reported. The initial severity grading may be updated in follow-up reports if the maximum grade changes to a higher level. The CTCAE grading scale should be used according the following guidelines.

Grade 1 (Mild)

Transient (< 48 hours) or mild discomforts, no or minimal medical therapy or intervention required, hospitalization not necessary, no or little limitation in normal activities, nonprescription or single-use prescription therapy may be employed to relieve symptoms (e.g., aspirin for simple headache, acetaminophen with codeine for post-surgical pain). Mild adverse events may be listed as expected consequences of the

therapy for any given protocol, and standard supportive measures for such an expected event do not necessarily elevate the event to a higher grade.

Grade 2 (Moderate)

Mild to moderate limitation in activity, some assistance may be needed; possibly none but usually minimal intervention/therapy required, hospitalization possible.

Grade 3 (Severe)

Marked limitation in activity, some assistance usually required; medical intervention/therapy required; hospitalization possible or likely.

Grade 4 (Life-Threatening)

Extreme limitation in activity, significant and immediate assistance required; significant medical/therapy intervention required to prevent loss of life; hospitalization, emergency treatment or hospice care probable. This grade is used when the subject was, in the view of the investigator, at substantial risk of dying at the time of the adverse event or it was suspected that use or continued use of the study agent would have resulted in the subject's death.

Grade 5 (Death)

Death related to AE.

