7.2.1.3 Adverse Event and Serious Adverse Event Reporting

All AEs, serious and non-serious, occurring during the course of the clinical trial (i.e., from signing the informed consent through the follow-up period) will be collected, documented, and reported to the sponsor by the investigator on the appropriate eCRF and SAE reporting forms.

For each AE, the investigator will provide the onset date, end date, seriousness, grade, relatedness, treatment required, outcome, and action taken with the study agent. The investigator will determine the grade as defined in [Section 7.2.1.2.3](#) and the causal relationship to the study agent (relatedness) as defined in [Section 7.2.1.2.4](#).

The investigator must report the following events immediately (within 24 hours or the next business day whichever is shorter) to the sponsor or designee (refer to the Lab Manual/ISF for specific instructions): SAEs and non-serious AEs relevant to the reported SAE and protocol-specified AESI.

The investigator does not need to actively monitor subjects for adverse events once the clinical trial has ended. However, if the investigator becomes aware of an SAE(s) that occurred after the subject has completed the clinical trial, it should be reported by the investigator to the sponsor if considered relevant by the investigator.

Any AE occurring during the study must be documented in the subject's medical records and as an AE in the eCRF. Any SAE occurring during the study must be documented in the subject's medical records and as an SAE in the eCRF.

A separate SAE report should be used for each SAE. However, if at the time of initial reporting, multiple SAEs are present that are temporally and/or clinically related, they may be reported on the same SAE report.

The investigator should attempt to establish a diagnosis of the event (that meets the definition of an AE or SAE) based on signs, symptoms, and/or other clinical information. In such cases, the diagnosis should be documented as the AE and/or SAE and not the individual signs or symptoms. The diagnosis will become the basis for the verbatim term as reported by the investigator. If no diagnosis is known and clinical signs and symptoms are not present, the abnormal finding should be recorded.

The investigator will take all appropriate and necessary therapeutic measures required for resolution of the AE. Any medication necessary for the treatment of an AE must be recorded on the concomitant medication case report form.

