8.2.1 SCREENING AND RUN-IN PERIOD

The screening period (Visit 1), i.e. the phase after informed consent and before the first administration of the study agent, may be as long as 6 days (day -7 to -2). However, a pretrial fundus photography/FA examination performed within 14 days prior to Visit 1 can be used as the screening ophthalmologic examination. In special cases where it is not logistically possible to meet the protocol defined screening period, the screening can be extended by an additional 7 days (day -14) without repeating the screening assessment.

The medical history and medication history within 3 months prior to Visit 1, as well as baseline condition of the subject, will be captured in the eCRF.

8.2.1.1 Visit 1

At Visit 1, the following procedures and assessments are performed:

- Signing of all applicable Informed Consents
- Potential study subject eligibility based on all study-specific inclusion and exclusion criteria (see [Sections 5.1](#) and [5.2](#))
- Demographics and medical history
- All ophthalmological evaluations: BCVA, SD-OCT, fundus photography/FA, slit lamp, and IOP (see [Sections 7.1](#) and [7.2.5](#))
- Vital signs, physical examination, safety laboratory tests, **Poland only**: serum pregnancy test (in women of childbearing potential), and 12-lead ECG (see [Sections 7.2.2](#), [7.2.3](#) and [7.2.4](#))
- Review of concomitant medications (see [Sections 6.3](#) and [6.4](#))
- AE reporting and evaluation according to [Section 7.2.1](#)

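### SAP 16.1 classes an adverse event that starts before first dose and worsens on ALK4290 as both treatment-emergent and not; if the onset rule is applied to a single updated record, the worsening is left out of the TEAE tables

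*SAP*

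**What the plan says.** Two adjacent sentences in SAP 16.1 define treatment emergence.

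- The worsening sentence: "All AEs that occur or worsen on or after the first use of IMP will be considered as treatment-emergent AEs (TEAE").
- The onset sentence: "Reported AEs that begin prior to the first dose of IMP are classified as non-TEAEs; these will only be included in subject listings". It adds that they are "not included in summary tables".

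The recording rules are in the protocol.

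- Protocol 7.2.1.3 collects AEs "from signing the informed consent through the follow-up period", so events that begin before dosing are expected in the database.
- On data items, the same section says: "For each AE, the investigator will provide the onset date, end date, seriousness, grade, relatedness, treatment required, outcome, and action taken". SAP 16.1 gives a similar list with start and end dates. Neither list has a date of worsening.
- Protocol 7.2.1.2.3 says "The highest severity grade experienced for the event should be reported" and "The initial severity grading may be updated in follow-up reports if the maximum grade changes to a higher level".
- Protocol 7.2.1.2.5 requires deterioration of the underlying disease or of another pre-existing condition to be entered as an AE or SAE.
- SAP 9.1 says that imputed dates are used in derivations and gives treatment-emergence status as its example.

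**The concern.** The two SAP sentences give opposite answers for one type of event, and the SAP does not say which governs. Two programmers could each follow the text and produce different AE tables.

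Incidence, seriousness and severity of AEs form the only secondary endpoint, and the planned AE tables (SAP 24, Tables 14.3.1.1 to 14.3.7.2) are almost all titled as TEAE tables. If the onset sentence is the one programmed, its effect on those tables can only be to remove on-drug deterioration, never to add it. The trial has a single arm, so no comparison group would show that this had happened.

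The situation can arise here. Screening runs from Day -7 to Day -2 and can be extended back to Day -14 (Protocol 8.2.1). It includes fluorescein angiography, for which Protocol 2.3.1 names allergic reactions as a risk.

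**Working it through.** The plan states no figure on this point, so there is nothing to reproduce. The check applies the two sentences as rules, then asks what the recorded data can support.

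**1. Classification under each sentence of SAP 16.1**

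| Type of AE | Worsening sentence | Onset sentence | Result |
|---|---|---|---|
| Starts on drug | TEAE | does not apply | consistent |
| Starts before dose, does not worsen | not a TEAE | non-TEAE | consistent |
| Starts before dose (e.g. Day -3), worsens on drug (e.g. Day 10) | TEAE | non-TEAE | contradiction |

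Only the third type is affected.

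**2. Can the worsening be derived?** Suppose the site keeps one record and raises its grade, as Protocol 7.2.1.2.3 allows. On the listed items, that record holds a pre-dose onset date, an end date and the maximum grade. Nothing on it dates the rise in grade relative to first dose. A date-based derivation then sees only the pre-dose onset, and the worsening limb of the first sentence cannot be applied. Suppose instead the site opens a new record at worsening. Its onset is on drug, and both sentences make it a TEAE. The result therefore depends on a recording choice that the two documents do not fix for events arising after consent.

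**3. Size per subject.** Planned enrolment is 30 (Protocol 10.5, SAP 6). Assuming all 30 are dosed, one subject is 1/30 = 3.3 percentage points. SAP 16.1 counts subjects and not events, so a row moves by this amount only if the subject has no other TEAE counted in it.

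**4. How likely is at least one such subject?** The documents give no rate, so the rate p below is an assumption shown over a range. P(at least one) = 1 - (1 - p)^30 and the expected number is 30p.

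| Assumed p | P(at least one of 30) | Expected subjects |
|---|---|---|
| 1% | 26% | 0.3 |
| 3% | 60% | 0.9 |
| 5% | 79% | 1.5 |
| 10% | 96% | 3.0 |

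These are illustrations of scale and not estimates.

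**The case against.** The strongest reply is that the onset sentence should be read as the residual rule: began before dose and did not worsen. That reading gives both sentences effect, and the event is tabulated. It is sensible and probably what was meant, but the sentence contains no such limit.

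Second, Protocol 7.2.1.2.5 has worsening of a pre-existing condition entered as an AE. If a screening-period event counts as pre-existing at first dose, its worsening may already get its own record with an on-drug onset. This stands as a possible route. However, the section does not say whether an AE arising after consent is a pre-existing condition, or that a new onset date is assigned, and it does not reconcile the SAP sentences.

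Third, a reader might infer that the recording rule keeps the pre-dose onset date, so that worsening is certain to vanish from every TEAE table. The documents do not support that. Protocol 7.2.1.2.3 concerns grade only and says the grade may be updated. No text says the onset date is retained. The item lists are not declared complete, and the eCRF and Data Management Plan are not in the two documents.

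Fourth, the deterioration would not be invisible. All AEs are listed (Listings 16.2.7.1 to 16.2.7.5), which is readable for 30 subjects, and slit-lamp, laboratory and ECG shifts, IOP thresholds and BCVA loss categories are tabulated whatever the TEAE status. This limits the harm but does not correct the AE tables.

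**Conclusion.** The contradiction in SAP 16.1 is real and on the face of the text. The consequence is conditional: on-drug worsening is left out of the TEAE tables if the onset sentence governs and the site has updated one record. Under the worsening sentence, or with a new record at worsening, it is tabulated.

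The scope is narrow: events that start between consent and first dose and then worsen. Abnormal ECG findings at screening are recorded as baseline conditions (Protocol 7.2.3), which narrows it further.

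The number of affected events cannot be known from the documents. A reader might take screening's share of the AE collection period as the size of the problem: 7/(7 + 71) = 9.0%, or 14/(14 + 71) = 16.5% when screening is extended. That is a share of calendar time, not of events, and should not be used so. The supportable figure is 3.3 points per affected subject at 30 subjects, for rows where that subject has no other TEAE. The point merits correction because it bears on the secondary endpoint and the correction is cheap.

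**What to change.** 1. In SAP 16.1, limit the onset sentence to AEs that begin before first dose and do not increase in grade or become serious on or after it.
2. In the eCRF completion guideline, and consistently with Protocol 7.2.1.2.5, state that worsening of a pre-dose AE on or after first dose is entered as a new record with its own date and grade. Say that the grade-update provision of Protocol 7.2.1.2.3 is not used in that case.
3. Before database lock, query AEs with pre-dose onset that were still ongoing at Day 1 and whose grade later rose or which later became serious, and obtain the date of the change.

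The cost is one SAP clause, one guideline instruction and a few queries. Reported TEAE rates may rise slightly. Classification of the other two event types does not change.
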